4.1.	Primary outcome	6
4.2.	. Secondary outcomes	6
4.3.	. Safety outcomes	7
5. H	Iandling of missing values	8
6. St	Statistical analyses	8
6.1.	. Primary analysis	9
6.2.	. Secondary analyses	9
6.3.	. Safety analysis	11
6.4.	. Example table of baseline characteristics	11

1. Study objective

A significant proportion of COVID patients experience persistent long-term symptoms (1-4), including cognitive deficits in attention, executive functions and memory (3,5,6). These cognitive impairments can impact daily living abilities, quality of life, and working capacity. Currently, there are no evidence-based treatment approaches for cognitive symptoms following post-COVID. Cognitive training interventions are a promising approach to counteract cognitive impairment (7-10). Moreover, transcranial direct current stimulation (tDCS) may enhance the effects of behavioral training, improve the consolidation of training outcomes, and facilitate transfer to other cognitive domains (11-13). However, the efficacy of cognitive training alone or in combination with tDCS on cognitive performance, quality of life, and mental health has not been evaluated in post-COVID patients with subjective or objective cognitive decline. The Neuromod-COV trial (14) aims to fill this gap by assessing the immediate and delayed effects of cognitive training, with or without concurrent tDCS, on cognitive performance, quality of life and mental health in patients experiencing post-COVID subjective or objective cognitive impairments.

The analyses described in this Statistical Analysis Plan will evaluate the efficacy of a threeweek cognitive training intervention with or without concurrent tDCS in patients with post-COVID cognitive impairments. This SAP has been prepared following the Guidelines for the Content of Statistical Analysis Plans in Clinical Trials (15). The trial will be reported following the Consolidated Standards of Reporting Trials [CONSORT (16)].

1.1. Study design

This study is a monocentric, prospective, randomized, open-blinded endpoint (PROBE) (17) phase II clinical trial designed to evaluate the effectiveness of a cognitive training intervention compared to a control intervention [Progressive Muscle Relaxation; PMR (18)] in patients with post-COVID subjective or objective cognitive impairment (primary endpoint).

Patients with post-COVID cognitive impairment participate in a three-week intervention program consisting of nine sessions (three per week) of either cognitive training or PMR (18) (open-label interventions). In the cognitive training group, participants are further divided into two subgroups: half receive anodal tDCS while the other half receive sham tDCS in a double-blinded, sham-controlled manner (secondary endpoint). Thus, participants are randomly allocated to one of three study arms: (1) cognitive training with anodal tDCS over the left dorsolateral prefrontal cortex (DLPFC); (2) cognitive training with sham tDCS over the left DLPFC; or (3) PMR with sham tDCS.

Random allocation to these three groups is done through a stratified block randomization method with variable block length, using a 1:1:1 ratio. The stratification is based on participants' performance in the n-back task during pre-assessment, with two strata: those scoring $\leq 87\%$ correct and those scoring > 87% correct. The randomization sequences are generated software's blockrand package using the R (https://CRAN.Rproject.org/package=block- rand; http://www.R-project.org). Following a telephone screening and baseline assessment, eligible participants who provide written informed consent are randomly assigned to a study arm according to the generated randomization sequence within each block and performance stratum.

Secondary hypotheses related to the comparison of the two cognitive training arms with active or sham tDCS, will be evaluated in a double-blinded, sham-controlled manner.

[figure not shown]

Figure 1. Neuromod-COV study flowchart. tDCS: transcranial direct current stimulation; PMR: Progressive Muscle Relaxation. Obtained from Neuromod-COV study protocol (14).

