1.4. Sample size calculation

The power calculation is based on recent studies using multi-session cognitive training interventions compared to control training (19–21), focusing on immediate performance in the trained task. Based on these findings, we estimated an effect size of Cohen's d = 0.8. To detect an effect in the primary outcome (percentage of correct responses on the n-back task between the cognitive training and control PMR groups) using an independent t-test with a two-sided significance level of $\alpha = 0.05$ and a power of at least 80%, 60 participants are required. This includes 40 participants for the cognitive training groups (for secondary comparisons of training combined with anodal vs. sham tDCS) and 20 participants for the PMR group. Even though we intend to analyze the primary outcome using covariance models, a conservative t-test approach was chosen for the power calculation. The sample size was estimated using the R software's *pwr* package (https://cran.r-project.org/package=pwr, http://www.R-project.org). This monocentric clinical trial will enable us to calculate the sample size for a subsequent multicenter clinical trial applying tDCS-accompanied cognitive training.

2. Analysis sets

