6.2. Secondary analyses

Effects of cognitive training vs. PMR

- Treatment effects on the transfer task (n-back task) at follow-up assessment will be examined by estimating marginal means (and 95% CI) from the model above.
- Treatment effects on the training task (letter updating task) at post- and follow-up assessments will be analyzed using a linear mixed-effects model. This model will include the letter updating performance at post- and follow-up assessments (number of correctly recalled lists) as the dependent variable. Fixed effects will include group (cognitive training vs. PMR) and measurement time point (post vs. follow-up). Control covariates will include the letter updating performance at pre-assessment (number of correctly recalled lists), age, and sex. A random intercept for subjects will also be included. Immediate and sustained training effects at post- and follow-up assessments will be estimated via marginal means (95% CI) from this model.
- Treatment effects on the visuospatial memory task (virtual reality task) at post- and followup assessments will be analyzed using a linear mixed-effects model. This model will include the virtual reality task performance at post- and follow-up assessments (number of goals reached) as the dependent variable. Fixed effects will include group (cognitive training vs. PMR) and measurement time point (post vs. follow-up). Control covariates will include the virtual reality task performance at pre-assessment (number of goals reached), age, and sex. A random intercept for subjects will also be included. Immediate and sustained effects on visuospatial memory performance at post- and follow-up assessments will be estimated via marginal means (95% CI) from this model.
- Treatment effects on working memory discrimination (n-back task d'prime scores) at postand follow-up assessment will be analyzed using a linear mixed-effects model. This model will include the n-back d'prime scores at post-and follow-up assessments as the dependent variable. Fixed effects will include group (cognitive training vs. PMR), measurement time point (post vs. follow-up) and task difficulty (1-back vs. 2-back). Control covariates will include the n-back d'prime scores at pre-assessment, age, and sex. A random intercept for subjects will also be included. Immediate and sustained effects on working memory discrimination at post- and follow-up assessments will be estimated via marginal means

(95% CI) from this model.

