- Treatment effects on health-related quality of life (PROMIS® PROPr scores) at post- and follow-up assessment will be analyzed using a linear mixed-effects model. This model will include the PROMIS® PROPr scores at post-and follow-up assessments as the dependent variable. Fixed effects will include group (cognitive training vs. PMR) and measurement time point (post vs. follow-up). Control covariates will include the PROMIS® PROPr scores at pre-assessment, age, and sex. A random intercept for subjects will also be included. Immediate and sustained effects on health-related quality of life at post- and follow-up assessments will be estimated via marginal means (95% CI) from this model.
- Treatment effects on subjective cognitive functioning (PROMIS® T-scores) at post- and follow-up assessment will be analyzed using a linear mixed-effects model. This model will include the PROMIS® cognitive functioning T-scores at post-and follow-up assessments as the dependent variable. Fixed effects will include group (cognitive training vs. PMR) and measurement time point (post vs. follow-up). Control covariates will include the PROMIS® cognitive functioning T-scores at pre-assessment, age, and sex. A random intercept for subjects will also be included. Immediate and sustained effects on subjective cognitive functioning at post- and follow-up assessments will be estimated via marginal means (95% CI) from this model.
- Treatment effects on the post-COVID functional status (PCFS total raw scores) at post- and follow-up assessment will be analyzed using a linear mixed-effects model. This model will include the PCFS total raw scores at post-and follow-up assessments as the dependent variable. Fixed effects will include group (cognitive training vs. PMR) and measurement time point (post vs. follow-up). Control covariates will include the PCFS total raw scores at pre-assessment, age, and sex. A random intercept for subjects will also be included. Immediate and sustained effects on post-COVID functional status at post- and follow-up assessments will be estimated via marginal means (95% CI) from this model.

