- Treatment effects on the sleep efficiency levels (sleep efficiency percentage) at postassessment will be analyzed using a linear mixed-effects model. This model will include the sleep efficiency percentage at post-assessment as the dependent variable. Fixed effects will include group (cognitive training vs. PMR). Control covariates will include the sleep efficiency percentage at pre-assessment, age, and sex. A random intercept for subjects will also be included.

Effects of cognitive training with active vs. sham tDCS

We will use the same analytical approach to assess the effects of active versus sham tDCS on all outcomes, replacing the group effect (cognitive training vs. PMR) with the stimulation group variable (active vs. sham tDCS). The only exception will be the analysis of treatment effects on the training task (letter updating task), which will be examined using the following two linear mixed-effects models:

• The first model will assess the treatment effects on the training task (letter updating task) at training- and post- assessments. This model will include the letter updating performance across all training and post-assessments (number of correctly recalled lists in sessions from V2 to V11) as the dependent variable. Fixed effects will include the stimulation group (active vs. sham tDCS) and measurement time point (V2 to V11). Control covariates will include

the letter updating performance at pre-assessment (number of correctly recalled lists), age, and sex, along with a random intercept for subjects. Training and immediate post-assessment effects will be estimated through marginal means (95% CI) from this model.

• The second model will evaluate the treatment effects on the training task (letter updating task) at follow-up assessment. This model will include the letter updating performance at post- and follow-up assessments (number of correctly recalled lists) as the dependent variable. Fixed effects will include group (active vs. sham tDCS) and measurement time point (post vs. follow-up). Control covariates will include the letter updating performance at pre-assessment (number of correctly recalled lists), age, and sex. A random intercept for subjects will also be included. Sustained training effects at follow-up assessment will be estimated via marginal means (95% CI) from this model.

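### Randomisation is stratified by pre-assessment n-back performance, but the secondary models for the non-n-back outcomes omit it, so linear-model intervals are somewhat conservative wherever the stratum is prognostic

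*SAP*

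**What the plan says.** Section 1.1 of the SAP describes a "stratified block randomization method with variable block length, using a 1:1:1 ratio". The only stratification factor is "performance in the n-back task during pre-assessment, with two strata": at most 87% correct, and above 87% correct.

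Section 6.2 then fixes the covariates outcome by outcome:

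- Letter updating: "Control covariates will include the letter updating performance at pre-assessment (number of correctly recalled lists), age, and sex".
- Virtual reality, PROMIS PROPr and PROMIS cognitive function: the same pattern, each with its own pre-assessment value.
- PCFS: the entry starts "Control covariates will include the PCFS total raw scores at" pre-assessment and goes on to age and sex.
- Sleep efficiency: "Control covariates will include the sleep efficiency percentage at pre-assessment, age, and sex".

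For active versus sham tDCS, section 6.2 carries the same approach over with the group variable replaced. It writes out two separate letter updating models, which also adjust only for own baseline, age and sex. That makes 6 models for training versus PMR and 7 for active versus sham, 13 in all, without the stratification factor.

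The primary model in section 6.1 is different. It adjusts for pre-assessment n-back percentage correct, so it largely carries the stratification information. The d-prime model adjusts for pre-assessment d-prime, a close relative. The end of section 6.2 leaves the link function open by scale (logistic, linear or ordinal) and declares all secondary analyses exploratory.

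**The concern.** Blocking within strata makes the arms nearly equal on the stratification factor. If that factor predicts the outcome, the between-stratum variation largely drops out of the true sampling error of the treatment difference. A linear model that does not know the stratum still counts this variation as residual error, or as random-intercept variance in the mixed models. Its standard error is then larger than the real one, its intervals cover more than 95%, and its tests reject less often than the nominal level.

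Precision is at stake. The active versus sham comparison has about 20 participants per arm. Letter updating is presented as trained working memory and the n-back as untrained working memory, so some shared variance beyond own baseline is plausible there, and also for the virtual reality memory task. The SAP itself fixes both the randomisation scheme and the covariates, and the two do not match.

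**Working it through.** **1. The plan's own figure.** Section 1.4 states "we estimated an effect size of Cohen's d = 0.8" and "a power of at least 80%, 60 participants are required"; "This includes 40 participants for the cognitive training groups", with 20 for PMR. For a two-sided t-test at 0.05, the noncentrality is 0.8 × √(40 × 20 / 60) = 2.92 on 58 degrees of freedom. Power is 81.9%. With 38 versus 19 it is 79.9%, so 60 reproduces. This gives the arm sizes used below: 40 versus 20 for training versus PMR, and 20 versus 20 for active versus sham.

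**2. The missing input.** Let R² be the share of outcome variance that the stratum explains after own baseline, age and sex. The SAP gives no value. R² is therefore an assumption, taken from 0% to 15%.

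**3. Size in a linear model.** With good balance within strata, in large samples:

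- Ratio of reported to correct standard error: 1/√(1 − R²).
- True type I error of a nominal 5% test: 2[1 − Φ(1.96/√(1 − R²))].

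| Assumed R² | 1/√(1 − R²) | Simulated SE ratio, 20 vs 20 | Type I error (formula) |
|---|---|---|---|
| 0% | 1.000 | not run | 5.0% |
| 2% | 1.010 | 1.010 | 4.8% |
| 5% | 1.026 | 1.028 | 4.4% |
| 10% | 1.054 | 1.058 | 3.9% |
| 15% | 1.085 | 1.090 | 3.4% |

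The simulated column comes from 8,000 trials per row, balanced within two strata. It lies slightly above the formula because the samples are small. With exact balance, the omitted-stratum residual variance is R² × 40/38 + (1 − R²); at R² = 10% the ratio is √(1.0053/0.90) = 1.057. The rounded widening is therefore about 0%, 1%, 3%, 6% and 9%.

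The simulated type I errors were 4.5%, 4.5%, 3.9% and 3.4% for R² of 2% to 15%. The Monte Carlo standard error is √(0.05 × 0.95 / 8,000) = 0.24 points, so the 4.5% at R² = 2% is compatible with the formula's 4.8%, which is the figure to use.

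**4. Check under the plan's randomisation.** A separate simulation used 6,000 trials per setting: 60 participants, two strata, permuted blocks of 3, 6 or 9 (assumed lengths), 1:1:1, no treatment effect, and own baseline, age and sex in every model. Here ρ is the partial correlation of stratum and outcome, so R² = ρ². Results for training versus PMR:

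| ρ | R² | CI width ratio, omitted / included | Coverage, stratum omitted |
|---|---|---|---|
| 0 | 0% | 1.00 | 94.6% |
| 0.1 | 1% | 1.00 | 94.5% |
| 0.2 | 4% | 1.02 | 95.4% |
| 0.3 | 9% | 1.05 | 96.0% |
| 0.4 | 16% | 1.09 | 96.6% |
| 0.5 | 25% | 1.16 | 97.6% |

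Active versus sham gives practically the same ratios (1.05 at ρ = 0.3, about 1.16 at 0.5). At ρ = 0.3 the mean half-width there is 0.665 without the stratum and 0.636 with it, in SD units of the outcome after own baseline, age and sex. With the stratum in the model, coverage stays near 95% throughout. At ρ = 0, adding it leaves the width essentially unchanged.

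**5. Limits of the check.** The simulation in step 4 uses one time point per participant, not the full post and follow-up mixed model. The stratum is a between-subject factor, so the direction carries over. Neither step covers an ordinal or logistic model.

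**The case against.** The strongest reply is that the document contains nothing to show the stratum is prognostic once own baseline is in the model. A cut in task accuracy at 87% has no evident link to actigraphy sleep efficiency, PROPr, the PROMIS cognitive T-score or PCFS beyond each outcome's own earlier value. Even for letter updating, the pre-assessment letter updating score is itself a working-memory measure and may absorb part of what a two-level n-back split carries. At R² near zero there is no widening. This stands. A reader might infer that the intervals of all six outcomes are too wide, but the SAP supports only a conditional statement, with the emphasis on the two cognitive tasks.

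The mechanism is also specific to linear models. If PCFS is analysed with an ordinal or logistic link, as section 6.2 allows, leaving out a prognostic covariate mainly pulls the conditional effect toward zero, and the percentages above do not apply. This too stands.

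Third, the analyses are exploratory and mostly reported as marginal means with 95% intervals. Section 6.2 sets no significance threshold, so the type I error figures describe how conservative the intervals are. They do not describe a decision rule.

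Finally, a reader might infer that the n-back score is also missing from the multiple imputation. Section 5 lists no imputation variables, so that cannot be established.

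None of this supplies a reason for leaving out the one factor by which the trial randomises.

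**Conclusion.** The mismatch is real and its consequence is small. Thirteen secondary models omit the stratification factor without a stated reason. In linear models, the intervals are about 1% to 9% too wide if the stratum explains 2% to 15% of the residual variance, and not too wide if it explains none. These figures rest on assumed values of R², on good balance within strata, and on a linear link.

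A reader might take this as a threat to validity. The documents do not support that: in the linear case there is no bias and no excess of false positives, and the primary n-back analysis already adjusts for pre-assessment n-back performance. The severity is low; it is a nearly free improvement to exploratory analyses, most useful for letter updating and virtual reality.

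**What to change.** In section 6.2, add the continuous pre-assessment n-back percentage, or the two-level stratum, as a fixed covariate in the models for letter updating, virtual reality, PROMIS PROPr, PROMIS cognitive function, PCFS and sleep efficiency. Do this for both comparisons, including the two separate letter updating models for active versus sham. If the sponsor prefers to leave it out for some outcomes, one sentence should say why.

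The cost is one line of text and one degree of freedom per model. The score is needed before allocation, so it is available for every randomised participant, and no new data are required.

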1.2. Primary hypothesis

• Cognitive training, combined with either active or sham tDCS, will result in greater improvement in untrained working memory performance at post-assessment compared to the control group receiving PMR in post-COVID patients. This outcome is operationalized by the percentage of correct responses on the n-back task at post-assessment.

1.3. Secondary hypotheses

• Cognitive training with either active or sham tDCS will result in greater improvements at post- and follow-up assessments compared to the control group (PMR) in post-COVID patients across multiple domains: (a) untrained working memory, measured by the percentage of correct responses on the n-back task (transfer task); (b) trained working memory, measured by the number of correctly recalled lists on the letter updating task; (c) visuospatial memory, measured by the number of goals reached on the virtual reality task; (d) working memory discrimination, measured by the d-prime scores on the n-back task; (e) health-related quality of life, measured by the preference-based scores (PROPr scores) on the Patient Reported-Outcomes Measurement Information System (PROMIS®) 29-Profile v2.1; (f) subjective cognitive functioning, measured by the T-scores on the PROMIS®

Cognitive Function Scale (short form 8a - v2.0); (g) post-COVID functional status, measured by the total raw scores on the Post-COVID Functional Scale (PCFS); and (h) sleep efficiency levels, measured as the percentage of time spent asleep relative to total time in bed, as recorded by an actigraphy device.

These outcomes will be assessed at post- and follow-up assessments, except for (a) untrained working memory, which will be evaluated only at the follow-up assessment, and (g) sleep efficiency levels, which will only be measured at the post-assessment.

• Cognitive training with active tDCS will result in greater improvements at post and follow-up assessments compared to cognitive training with sham tDCS in post-COVID patients across multiple domains: (a) untrained working memory, measured by the percentage of correct responses on the n-back task (transfer task); (b) trained working memory, measured by the number of correctly recalled lists on the letter updating task; (c) visuospatial memory, measured by the number of goals reached on the virtual reality task; (d) working memory discrimination, measured by the d-prime scores on the n-back task; (e) health-related quality of life, measured by the PROPr scores on the PROMIS® 29-Profile v2.1; (f) subjective cognitive functioning, measured by the T-scores on the PROMIS® Cognitive Function Scale (short form 8a - v2.0); (g) post-COVID functional status, measured by the total raw scores on the PCFS; and (h) sleep efficiency levels, measured as the percentage of time spent asleep relative to total time in bed, as recorded by an actigraphy device.

These outcomes will be assessed at both post and follow-up assessments, except for the (g) sleep efficiency levels, which will only be measured at post-assessment.

